8. RANDOMISATION

Patients must be randomised centrally by the trials unit (ICR-CTSU) before trial treatment can commence.

After RT planning at the local RT centre, sites will contact ICR-CTSU to obtain treatment allocation for a consented patient.

Patients should be randomised by emailing the ICR-CTSU randomisation service at:

[contact]

09.00-17.00 (UK time) Monday to Friday

Randomisation should take place as close to the planned start date of treatment as possible. An eligibility and randomisation checklist must be completed prior to randomisation.

The following information will be required at randomisation:

- Name of hospital, consultant and person registering patient
- Confirmation that patient has given written informed consent for trial and for any sub-studies;
- Confirmation that patient is eligible for the trial by completion of the eligibility checklist
- Patient's full name, hospital number, date of birth, postcode and NHS/CHI number
- IMN RT (yes/no), randomising centre, type of surgery (breast conserving surgery with axillary surgery / mastectomy with axillary surgery / axillary surgery only), breast reconstruction (none/autologous/non-autologous) and requirement for tumour bed boost irradiation (yes/no).
- Calculated lifetime risk of radiation-induced heart disease based on wide-tangent plan

The caller will be given the patient's unique randomisation number (Trial ID) and treatment allocation.

ICR-CTSU will send confirmation to the data management contact at the recruiting site to confirm a patient's entry into the trial.

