10. TRIAL ASSESSMENTS

10.1. Baseline Assessments (Pre-randomisation)

The following assessments should be conducted prior to randomisation

- Medical history (including specific risk factors for cardiovascular disease and RT toxicity)
- Weight and height
- Baseline signs and symptoms (CTCAE v5.0, RTOG)
- Patient-reported outcomes (PRO) of health-related quality of life (QoL) including EORTC QLQ-C30 and QLQ-BR23, Body Image Scale, protocol-specific questions relating to breast changes resulting from cancer treatments, PRO-CTCAE items, EQ-5D-5L, healthcare resource use to be collected prior to patient being aware of treatment allocation.
- Biological sample collection (tumour tissue collected from the diagnostic biopsy and/or surgery when requested and research bloods) for those patients providing optional consent

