14. STATISTICAL CONSIDERATIONS

14.1. Statistical Design and Sample Size Justification

Sample size justification for co-primary outcomes

The sample size requirements are driven by the co-primary outcome of patient-reported 2-year breast symptoms, hence this is considered first. A total of 192 patients (96 in each randomised group) would provide 92% power to exclude a 2-year mean breast symptoms subscale score (from EORTC QLQ-BR23) at least 10 points higher for PBT compared with tailored RT (assuming standard deviation (SD) =19 and 1-sided α =0.025 as testing for non-inferiority). Non-inferiority of PBT will be concluded if the upper 95% confidence limit for the difference between mean breast symptoms scores is <10. The sample size allows for 10% unevaluable for patient-reported outcome at 2 years, from experience with previous breast RT trials. A 10-point difference is usually considered a minimally important difference for EORTC quality of life scores.

A sample size of 192 patients provides ~99% power to detect a difference in mean heart dose of at least 1 Gy between PBT and tailored RT (assuming SD =1 Gy and 2-sided α =0.05); 1 Gy reduction in mean heart dose for PBT corresponds to an estimated 7.4% reduction in rate of major coronary events(10). The effect of PBT versus tailored RT should be shown for both co-primary outcomes in order to establish clinical benefit; the conjunctive power for this overall assessment is 91% (100 x 0.92 x 0.99).

Sample size justification for mechanistic outcomes

Sample size calculations for the mechanistic study are primarily based on validating published findings suggesting end of range RBE>1.1(41). This study compared pre- to post-treatment radiological lung changes in Hounsfield Units (HU) per Gray (HU/Gy) (RBE) between PBT and photons (N=10 in each group), with estimated mean difference of -1.08 (for PBT vs RT) and SD =1.1 (standardised effect size 0.98). Compared with Underwood's retrospective study, PARABLE's harmonised, prospective imaging will provide a far improved methodology for detecting post-treatment HU changes, hence it is possible that anticipated effect sizes in PARABLE may be larger than those in Underwood's study. Allowing for 10% unevaluable at 2 years, 96 patients per group (192 total) provides 90% power to detect standardised effect sizes >0.5 (mean difference >0.55 HU/Gy, SD 1.1) in terms of radiological lung changes from pre- to post-treatment, comparing PBT and tailored RT (2-sided α =0.05).

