14.2. Treatment Allocation

Patients will be allocated to PBT (in Manchester or London) versus tailored RT at local centre in a 1:1 ratio. Treatment allocation will use a minimisation algorithm with a random element, to ensure balanced distributions of clinically important factors (balancing factors) between treatment groups. Balancing factors will include IMN RT (yes/no), randomising centre, type of surgery (breast conserving surgery with axillary surgery / mastectomy with axillary surgery / axillary surgery only), breast reconstruction (none/autologous/non-autologous), and need for tumour bed boost.

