14.4. Statistical Analysis Plan

Statistical analysis plan for co-primary outcomes

Analysis of the co-primary outcomes will take place once all patients have reached the 2-year follow-up time point (or are known to have ceased follow-up). Mean heart dose and mean 2-year breast symptoms scores will each be compared between PBT and tailored photon RT using a 2-sample t-test, and 2-sided 95% confidence intervals for the mean differences calculated. Non-inferiority of PBT for patient-reported breast symptoms at 2 years will be concluded if the upper 95% confidence limit for the difference between mean breast symptoms scores is <10; a superiority test will be carried out if

non-inferiority is shown. Although the primary analysis of the co-primary outcomes will be non-stratified, consideration will also be given in the statistical analysis plan to sensitivity analyses including adjustment for balancing and other prognostic factors. Mean heart dose data should be available for all trial participants, as this will be obtained from the RT treatment plans. Missing data for the patient questionnaires can occur in terms of missing responses to individual items or entire questionnaires not returned. The EORTC quality of life scoring manual specifies approaches for dealing with missing data. If a significant proportion of patients are not evaluable for 2-year patient-reported breast symptoms, missing data patterns will be assessed, e.g. by comparing characteristics of patients with and without 2-year questionnaires. If there appear to be differences between evaluable/non-evaluable patients, a sensitivity analysis for the co-primary patient-reported outcome assuming different missing data patterns may be performed.

Statistical analysis plan for secondary outcomes

Analyses of dosimetry outcomes (mean heart, lung and contralateral breast doses) will be done once all patients have completed their RT/PBT treatment. Analysis of mean lung and contralateral breast doses will use the same methods as described for mean heart dose.

Acute toxicity data will be analysed once all patients have reached 6 months after RT/PBT. Key time points for analysis of the other secondary outcomes including late toxicities and disease-related outcomes will be at 2 and 5 years.

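### The primary test of 2-year breast symptoms is unadjusted, so it forgoes precision available from the baseline score and the minimisation factors

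*Protocol*

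**What the plan says.** Section 14.4 states that the two co-primary outcomes will "each be compared between PBT and tailored photon RT using a 2-sample t-test", with two-sided 95% confidence intervals. PBT is non-inferior on breast symptoms if the upper limit for the difference is below 10 points. The same section labels this choice plainly: "Although the primary analysis of the co-primary outcomes will be non-stratified". Adjusted analyses appear there only as a possibility, in these words: "consideration will also be given in the statistical analysis plan to sensitivity analyses including adjustment for balancing and other prognostic factors". It gives no reason for leaving the primary analysis unadjusted.

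On allocation, section 14.2 says: "Treatment allocation will use a minimisation algorithm with a random element". The factors are IMN radiotherapy, randomising centre, type of surgery, breast reconstruction and tumour bed boost.

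Section 10.1 lists among the pre-randomisation assessments: "Patient-reported outcomes (PRO) of health-related quality of life (QoL) including EORTC QLQ-C30 and QLQ-BR23, Body Image Scale". The baseline value of the co-primary score is therefore planned for collection before the patient knows the allocation.

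On sample size, section 14.1 says: "A total of 192 patients (96 in each randomised group) would provide 92% power". Its inputs are given as "assuming standard deviation (SD) =19 and 1-sided α =0.025 as testing for non-inferiority", with a 10-point margin and an allowance of 10% unevaluable.

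**The concern.** Two separate sources of precision go unused in the decisive comparison.

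- **Baseline score.** If breast symptoms before radiotherapy predict symptoms at 2 years, conditioning on them reduces the residual variance. The t-test leaves that variance in the standard error.
- **Minimisation factors.** If they are prognostic, forcing balance on them reduces the true sampling variability of the difference in means. The t-test does not credit this, so its standard error is too large and the test is conservative.

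Non-inferiority depends on one confidence limit, so interval width bears directly on the conclusion. The planned power assumes a true difference of zero. Section 1.1.4 reports non-randomised evidence of more skin reactions with PBT, and section 14.3.1 says the breast symptoms scale covers skin problems. A small true excess within the margin is therefore conceivable, and there the power has less room. Section 14.4 also foresees adjustment, where appropriate, in the longitudinal and time-to-event toxicity models, so some secondary analyses may use more information than the co-primary.

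**Working it through.** **Inputs from section 14.1.** 96 per arm with 10% unevaluable gives 0.9 × 96 = 86.4, taken as 86 per arm. SD 19, margin 10, one-sided α 0.025.

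**Reproducing the stated power.** SE = SD × √(2/n) = 19 × √(2/86) = 2.90. Half-width = 1.96 × 2.90 = 5.68 points. Power at zero difference = Φ(10/2.90 − 1.96) = 93.2% (92.9% by noncentral t). This agrees with the stated 92%, so the planned power belongs to the unadjusted test and is met by it.

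**Adjusting for the baseline score.** Residual SD = 19 × √(1 − ρ²), where ρ is the baseline-to-2-year correlation. The protocol gives no ρ, so the values below are assumptions. The 2-point excess is likewise an illustration. The last column is the total N for 92% power at zero difference with 10% unevaluable.

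| ρ | Residual SD | SE | Half-width | Power, true difference 0 | Power, PBT 2 points worse | N for 92% |
|---|---|---|---|---|---|---|
| 0 (t-test) | 19.00 | 2.90 | 5.68 | 93.2% | 78.8% | 184 |
| 0.3 | 18.12 | 2.76 | 5.42 | 95.1% | 82.5% | 168 |
| 0.5 | 16.45 | 2.51 | 4.92 | 97.9% | 89.0% | 138 |

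The interval narrows by 1 − √(1 − 0.09) = 5% at ρ = 0.3 and by 1 − √(1 − 0.25) = 13% at ρ = 0.5.

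**Effect of minimisation.** This was simulated with 172 evaluable patients and 3,000 runs (Monte Carlo SE about 0.3 percentage points for the error rate). Minimisation used the five factors, 22 equal centres and an 80% chance of following the preferred arm. Factor prevalences were assumed, and centre itself was given no effect. The adjusted model held the baseline score and the four factors other than centre. R² is the share of outcome variance explained by those four factors.

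| R² | ρ | One-sided error at margin: t-test / adjusted | Power at 0: t-test / adjusted | Half-width: t-test / adjusted |
|---|---|---|---|---|
| 0 | 0 | 2.7% / 2.4% | 93.0% / 92.8% | 5.71 / 5.75 |
| 0.05 | 0.3 | 2.4% / 2.4% | 93.8% / 96.0% | 5.72 / 5.34 |
| 0.10 | 0.3 | 1.8% / 2.4% | 93.9% / 96.5% | 5.72 / 5.18 |
| 0.10 | 0.5 | 2.0% / 2.6% | 93.7% / 98.9% | 5.72 / 4.63 |
| 0.20 | 0.5 | 1.7% / 2.3% | 94.7% / 99.4% | 5.71 / 4.26 |

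At R² of 10-20% the t-test is conservative (1.7-2.0% against 2.5%) and the adjusted model is close to nominal. At 5% no conservatism is visible. With nothing prognostic, the methods are equivalent.

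**Mean heart dose.** For 1 Gy, SD 1 Gy and 96 per arm, SE = √(2/96) = 0.144 Gy. Power = Φ(1/0.144 − 1.96), above 99.99%, with or without adjustment. The half-width is 0.283 Gy unadjusted, and 0.270 or 0.245 Gy at assumed correlations of 0.3 or 0.5.

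**The case against.** The strongest defence is that nothing here is wrong. The test is pre-specified and matches the power calculation. Any error from ignoring balanced prognostic factors is in the cautious direction for a non-inferiority claim. Chance imbalance in baseline symptoms is already covered by the nominal interval. Adjusted sensitivity analyses are foreseen and left to the statistical analysis plan, where the other prognostic factors could include the baseline score. Every gain shown rests on a correlation or R² that the protocol does not supply, and at ρ = 0.3 it is only two points of power.

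All of that stands, and it makes this a point about efficiency. It does not remove the point. The protocol itself fixes the unadjusted primary analysis, and a favourable adjusted sensitivity analysis could not replace a primary upper limit that crosses 10.

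A reader might infer more than the documents support:

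- **Power is lost on both co-primaries.** For heart dose there is none to regain.
- **The analysis is invalid or the trial underpowered.** Type I error is not inflated, and the stated power reproduces.
- **The size loss follows from 2 × (1 − Φ(1.96/√(1 − R²))), or 3.9-2.8%.** That formula assumes perfect balance, whereas the minimisation has a random element. It is also on a two-sided 5% scale, whereas the decision is one-sided at 2.5%.
- **The wide-tangent dose is ready as a covariate.** The randomisation list in section 8 names "Calculated lifetime risk of radiation-induced heart disease based on wide-tangent plan". The dose in Gy must exist for eligibility, but its capture as trial data is not stated.

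**Conclusion.** For 2-year breast symptoms, the unadjusted primary analysis is valid but less precise than the design allows, provided the baseline score or the balancing factors are prognostic. At assumed correlations of 0.3-0.5, adjustment brings the half-width from about 5.7 to 5.4-4.9 points and power from about 93% to 95-98%. If PBT were truly 2 points worse, power would go from about 79% to 82-89%. If the balancing factors explain 10-20% of variance, the t-test runs at 1.7-2.0% one-sided error in the simulation. If nothing is prognostic, the two analyses are equivalent. Heart-dose power is virtually 100%, so any gain on breast symptoms passes almost unchanged into the power for showing both co-primaries. The change is worth making because it is cheap, not because the planned analysis would mislead.

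**What to change.** In section 14.4, and in the statistical analysis plan to match, make the primary analysis of 2-year breast symptoms a linear model with treatment, baseline breast-symptoms score, IMN radiotherapy, surgery type, reconstruction and boost. Handle randomising centre in a way suited to about 22 sites, such as a random effect. Apply the 10-point rule to the upper 95% limit of the adjusted difference, and use the same model for the superiority test that follows. Keep the t-test as the sensitivity analysis. Pre-specify a rule for missing baseline scores, so that no evaluable patient is dropped for lack of one. Make the change before any outcome comparison by arm is seen; section 14.5 plans no formal interim analysis.

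For mean heart dose, adjusting for the balancing factors is optional, for consistency and precision only. The wide-tangent dose could be added if the sponsor confirms that its value in Gy is captured.

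The cost is wording, a few degrees of freedom and the missing-baseline rule. It needs no extra patients, no new questionnaire and no change of margin.

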14.3.3.2 Correlation of RBE-weighted dose maps with radiological changes in lungs and ribs

In patients randomised to PBT, doses to lungs and ribs on RBE-weighted dose maps for the 3 selected variable and standard RBE 1.1 models will be compared with radiological changes in lungs (lung fibrosis) and ribs (rib fractures and/or increased rib density). Candidate RBE models have been selected representing a phenomenological approach (McNamara model(43)), LET-weighted dose (McMahon(42)) and a mechanistic approach (Microdosimetric-Kinetic (44)).

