Analyses of toxicity data will follow methods established in previous breast RT trials. Frequencies of early and late toxicities will be summarised at each time point and compared between treatment groups at specific time points using chi-squared test or Fisher's exact test as appropriate. Longitudinal models (e.g. generalised estimating equations) including all assessments over follow-up, and survival analyses of time to first moderate/marked adverse effect will be carried out with comparisons between treatment groups, and adjusting for balancing and other prognostic factors where appropriate. Event rates at key time points will be reported, with 95% confidence intervals.

Analyses of compliance (receipt of allocated intervention, delays and re-plans) will be largely descriptive, with proportions presented according to trial arm, along with 95% confidence intervals where appropriate.

Analyses of disease-related recurrence and survival outcomes will also be primarily descriptive due to rarity of events, which would likely preclude formal statistical comparisons.

Statistical analysis plan for mechanistic outcomes

Mechanistic outcomes will be analysed once all evaluable patients have reached 2 years' follow-up. Pre and post treatment median lung Hounsfield Units per Gy on CT will be compared between PBT and RT using the methodology of Underwood(41) and quantified using linear regression adjusting for mean lung dose. Candidate RBE models have been selected representing phenomenological approaches (McNamara model(43)) as well as different mechanistic approaches (McMahon(42) and Microdosimetric-Kinetic model(44)). Dose distributions incorporating each of the proposed RBE models will be calculated and associations with lung fibrosis and rib fractures assessed using multivariable logistic regression as per standard dose-volume/outcome modelling methodology. For

the comparison of planned and delivered dose to target and normal tissues, delivered dose will be calculated using deformable image registration and compared with dose from the planning CT in order to calculate percentage difference in dose. Non-inferiority of PBT compared with RT in terms of percentage difference between planned and accumulated dose will be tested using a t-test.

Analysis sets and subgroup analyses

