All analyses will be on an intention to treat basis, including patients in the group to which they were randomised. Since protocol deviations may bias tests of non-inferiority hypotheses a sensitivity analysis of the co-primary patient-reported outcome will be done using the per protocol population excluding major treatment deviations; non-compliance will be carefully monitored during the trial.

The trial is not powered for formal subgroup analyses. However exploratory analyses will investigate differences between the treatment groups according to clinical groups including the balancing factors. Descriptive analyses will check for any differences between RT centres in terms of patient or treatment characteristics, or outcomes.

Full details of analysis methods will be specified in a Statistical Analysis Plan in accordance with ICR-CTSU Standard Operating Procedures.

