14.6. Internal pilot

The internal pilot will assess trial progress at end of month 15 (9 months after accrual opens). Trial progress will be assessed by:

- Overall recruitment (total patients/month from expected 11 centres): red <2; amber 2-3; green >3
- Acceptance of randomised allocation: red <80%, amber 80-90%, green >90%

The internal pilot will be considered successful and the trial will continue as planned if both sets of criteria are "green". Where both recruitment and acceptance of allocated treatment are red, discussions will be held with the funder and trial oversight committees to establish where amendments could be put in place to address these issues. Where recruitment or acceptance is amber or red, screening logs will be reviewed and centres surveyed to understand and address reasons behind this, and findings discussed with funder and trial oversight committees. If either remains red by month 21, the trial will be considered unfeasible. Where either remains amber, recruitment and/or acceptance will be reviewed 3-monthly until green.

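### Intention to treat is applied to every analysis, and the accumulated-dose non-inferiority test has no companion analysis by beam delivered, so PBT-to-photon crossover would make that test anti-conservative

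*Protocol*

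**What the plan says.** Section 14.4, under the heading on analysis sets and directly after the mechanistic analysis plan, sets one rule: "All analyses will be on an intention to treat basis, including patients in the group to which they were randomised". It then acknowledges that deviations can bias non-inferiority tests and provides that "a sensitivity analysis of the co-primary patient-reported outcome will be done using the per protocol population excluding major treatment deviations". No other outcome gets such an analysis.

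The mechanistic plan contains two between-arm comparisons:

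- **Lung density change, HU/Gy.** Section 14.1: "Allowing for 10% unevaluable at 2 years, 96 patients per group (192 total) provides 90% power to detect standardised effect sizes >0.5". On the original scale this is a difference of 0.55 HU/Gy with an SD of 1.1.
- **Accumulated dose.** Section 14.4: "Non-inferiority of PBT compared with RT in terms of percentage difference between planned and accumulated dose will be tested using a t-test". Section 14.1 assumes a 9% planned-to-accumulated difference in mean heart dose for photons and aims to exclude more than 10% for PBT, with SD 2% and one-sided alpha 0.05.

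A third mechanistic endpoint lies within the PBT arm and is defined by allocation (14.3.3.2): "In patients randomised to PBT, doses to lungs and ribs on RBE-weighted dose maps".

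On non-receipt, the only figures are the pilot thresholds in 14.6, in per cent: "Acceptance of randomised allocation: red <80%, amber 80-90%, green >90".

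**The concern.** Intention to treat protects a comparison of treatment policies. The mechanistic hypotheses in section 2.4 are not about policies. They ask how lung tissue responds to a given proton or photon dose, and how closely delivered dose follows planned dose for each beam. A PBT-allocated patient who is treated with photons contributes a photon answer to both questions, and the stated rule files it under PBT.

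In a superiority test this dilution costs power. In a non-inferiority test it pulls the arms together and makes the claim easier to reach. Section 14.4 recognises that hazard for the patient-reported outcome but not for the other non-inferiority test that it specifies. At stake is the mechanistic claim that accumulated heart dose tracks planned dose about as well for protons as for photons.

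**Working it through.** **Inputs.** From 14.1: 96 per group with 10% unevaluable, so 96 × 0.9 = 86.4, taken as 86 per arm. HU/Gy: difference 0.55, SD 1.1 (0.5 SD), two-sided 0.05; the earlier study gave 1.08/1.1 = 0.98 SD. Accumulated dose: margin 10 − 9 = 1 percentage point, SD 2, one-sided 0.05. Assumption: a share c of the evaluable PBT arm was treated with photons and has photon-like outcomes. The range c = 5%, 10%, 20% is anchored to the pilot thresholds, because the protocol states no expected crossover.

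**Step 1: the plan's own figures.** SE = SD × √(2/86).
- HU/Gy: SE = 1.1 × √(2/86) = 0.168; 0.55/0.168 = 3.28; t-test power 90.3%, against 90% stated.
- Accumulated dose: SE = 2 × √(2/86) = 0.305; 1/0.305 = 3.28; one-sided t-test power 94.7%, against 94% stated.

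Both reproduce, and neither includes crossover.

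**Step 2: false non-inferiority for accumulated dose.** Put PBT as delivered exactly at the margin, a true difference of 1. By allocation the expected difference is 1 − c, and the PBT-arm variance becomes 4 + c(1 − c). Then SE_c = √[(4 + c(1 − c))/86 + 4/86], and the error rate is Φ(c/SE_c − 1.645).

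| c | SE_c | c/SE_c − 1.645 | False non-inferiority |
|---|---|---|---|
| 0 | 0.305 | −1.645 | 5.0% |
| 5% | 0.306 | −1.481 | 6.9% |
| 10% | 0.307 | −1.319 | 9.4% |
| 20% | 0.308 | −0.996 | 16.0% |

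A simulation of 50,000 trials using the t-test gave 4.9%, 9.3% and 15.7% at c = 0, 10% and 20%.

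**Step 3: power for HU/Gy.** In SD units with true effect d, the expected difference is d(1 − c) and SE = √[(1 + c(1 − c)d²)/86 + 1/86]. Power is from the noncentral t with 170 degrees of freedom.

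| c | d = 0.5: difference/SE | Power | d = 0.98: difference/SE | Power |
|---|---|---|---|---|
| 0 | 3.28 | 90.3% | 6.43 | >99.9% |
| 5% | 3.11 | 87.0% | 6.04 | >99.9% |
| 10% | 2.93 | 83.1% | 5.66 | >99.9% |
| 20% | 2.60 | 73.3% | 4.95 | >99.8% |

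**Step 4: grouping by modality delivered.** If switching is unrelated to outcome, the non-inferiority error returns to the nominal 5%. For HU/Gy at 0.5 SD the normal approximation (90.6% without crossover) gives 90.4% at c = 10% and 89.5% at c = 20%, against 83.5% and 73.8% by allocation.

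**Step 5: the within-PBT endpoint.** The RBE-model comparison needs a proton dose map for each patient. A photon-treated patient has none, so cannot enter, and drops out as unevaluable. Nothing is diluted; only the wording is off.

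**The case against.** The strongest reply is that the blanket sentence is loose drafting. Section 14.3.3.3 speaks of patients treated in the trial, appendix A2 compares proton with photon therapy patients, section 14.4 restricts the mechanistic analysis to evaluable patients, and full details are left to a statistical analysis plan that is not shown. This lowers the chance that analysis strictly by allocation was intended. But none of these passages says that patients are grouped by beam received, and any such grouping would have to be reconciled with an explicit rule for all analyses.

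Three further objections stand and limit the point:

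- A reader might infer that crossover hides the effect the mechanistic study was built to detect. It does not: 0.5 SD is the detection floor, and at the 0.98 SD being validated the power loss is negligible.
- A reader might infer from 14.6 that the pilot accepts 20% non-acceptance. It does not. Amber triggers review of screening logs, a survey of centres, discussion with funder and oversight committees, and 3-monthly review until green. Red persisting at month 21 makes the trial unfeasible. Section 14.4 also promises monitoring of non-compliance.
- A reader might conclude that intention to treat should be replaced by as-treated groups. Those groups would be partly self-selected, and the balancing factors in 14.2 include neither smoking nor COPD, both plausible influences on lung density. That argues for an additional analysis, not a substitute.

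The 16% figure is also a worst case: it needs 20% crossover, evaluable data from every switcher, and a true difference exactly at the margin.

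**Conclusion.** The point holds in a limited form. Section 14.4 states a rule that can bias a test it also states, and leaves that test without the safeguard its own reasoning calls for. The consequence that matters most is for accumulated-dose non-inferiority: an error rate of about 7%, 9% or 16% instead of 5% at 5%, 10% or 20% crossover. The HU/Gy loss, to 87%, 83% or 73%, applies only to effects near the detection floor.

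These figures assume one-way crossover from PBT to photons, photon-like outcomes in those who switch, and evaluable data from them. Switchers with no 2-year CT dilute nothing for HU/Gy, and with no crossover there is no effect at all. No co-primary or clinical conclusion depends on this, and the RBE-model comparison is not biased by it.

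**What to change.** In section 14.4, extend the per-protocol provision to the two between-arm mechanistic comparisons, HU/Gy and accumulated dose. Add for each an analysis by modality actually delivered, excluding courses that mixed modalities. The receipt endpoint counts a single fraction, so it cannot identify mixed courses by itself. Adjust this analysis for the balancing factors and for lung-relevant baseline factors already collected, such as smoking and COPD. Report it beside the intention-to-treat result, and conclude accumulated-dose non-inferiority only if both agree.

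As a wording correction only, define the RBE-model endpoint in sections 4.3 and 14.3.3.2 by patients treated with PBT instead of patients randomised to it.

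The cost is a few sentences and a little more analysis work. The delivered-modality comparison is not strictly randomised for the few who switch, which is why intention to treat stays alongside it. Requiring agreement also makes a non-inferiority conclusion slightly harder to reach.
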